9.4.3 ANALYSIS OF THE SECONDARY ENDPOINT(S)

Analysis of the secondary outcome:

- The need for additional Narcotic usage over 2 weeks between the 2 arms

All patients will be discharged with 12 standard narcotic pills for managing post-operative pain by needs. However, patients can request additional narcotic pain killers if needed. The needs for extra amount of pain reliever is an indicator of pain level and a secondary aim of the current study.

The need for additional narcotic usage is a binary-coded variable with values of 'yes' or 'no'. The rate/percentage of patients requesting additional narcotic medication will be calculated for each study arm, and compared in a 2 by 2 contingency table format using chi-square test or Fisher's exact test, as appropriate.

- Compare pain scores between each arm at 2 weeks post-operative visit

At the two-week post-operative visit, patients will be asked to fill out the brief pain inventory to indicate their current pain levels, as well as the mildest and worst pain scores within the past 24 hours. The pain scores will also be evaluated by Likert-pain scale (the same pain assessment tool used at POD1. The mean pain scores between the two arms will be compared by a two-sample t-test or a Wilcoxon rank-sum test, where appropriate. Statistical significance between the two arms is considered if the p-value for the tests are <0.05.

9.4.4 9.4.4 SAFETY ANALYSES

Patients will be screening for allergy to or contraindications to study medication. If they meet criteria and consent for the study, then each patient will be monitored for safety in multiple forms. For each patient, vital signs are monitored in the operating room and during recovery until discharge. Electrocardiogram monitoring will also be continuously ongoing in the operating room. Assessment of adverse events throughout hospital stay will be done by review of charts and discussion with other members involved in patient care.

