1 PROTOCOL SUMMARY

1.1 SYNOPSIS

Title:	Clinical effectiveness of pre-incision versus post-incision local anesthetic during laparoscopic/robotic sacrocolpopexy
Study Description:	To compare postoperative narcotic use and pain score with pre-incisional versus post-incisional injection of local anesthetic at trocar sites in robotic/laparoscopic-assisted sacrocolpopexy
Objectives:	
Primary objective: Comparing postoperative Likert pain scale between patients who received pre-incisional versus post-incisional local anesthetic on postoperative day oneSecondary objectives: Total narcotic use over two weeks between patients who received pre-incisional versus post-incisional local anesthetic. To compare the pain levels reported by patients on the brief pain inventory questionnaire at POD14 between the two study groups (pre-incisional vs post-incisional) by two sample t –test or Wilcoxon rank-sum test, where appropriate.

Endpoints:	Primary Endpoint: comparing Likert-pain scale scores between pre-incisional versus post-incisional local anesthetic on postoperative day one Secondary Endpoints: total narcotic use over two weeks between patients who received pre-incisional versus post-incisional local anesthetic and to compare brief pain inventory questionnaires at POD14 between the two study groups.
Study Population:	Sample size – 64 per arm; Female gender, age \geq 18 years old, general health status healthy
Phase:	N/A
Description of Sites/Facilities	Northwell Health sites (Lenox Hill Hospital, Southshore Hospital, Long Island Jewish Hospital, Northshore Hospital, Huntington Hospital, Plainview, Peconic, Mather). No hospital outside of the US.
Enrolling Participants:	Subcutaneous injection of 4-5mL of 0.25% Bupivacaine into skin before or after incision for trocar placement during robotic/laparoscopic- assisted sacrocolpopexy
Description of Study Intervention:	
Study Duration:	18 months
Participant Duration:	2 weeks

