1.2 SCHEMA

Visit 0

- New patient/Surgical discussion Visit
 - Screen potential for inclusion and exclusion criteria
 - If meets criteria
 - Pamphlet provided to patient in regard to study information

Visit 1

- Preoperative visit
 - Discuss study in further detail, answer questions after patient read pamphlet, risks/benefits discussed and offer patient participation
 - If patient consents:
 - First Brief Pain Inventory Questionnaire to fill out prior to surgery. The Narcotic Diary will be given to patient with the instructions to fill out after surgery and to document all narcotic pills used including provided and any additional.
 - If a patient is undecided, then will follow up by phone call prior to surgical day. If she decides after follow up phone call then will have patient sign consent on day of surgery

Visit 2

- Day of surgery

- If patient does not consent at preoperative visit, but decides to participate after follow up phone call:
 - Obtain consent if patient has agreed by phone call (phone call which is after preoperative visit) on the day of surgery
 - Provide narcotic diary and first Brief Pain Inventory Questionnaire to fill out (if patient has not already filled it out previously). Patient only needs to fill out one brief pain inventory questionnaire prior to surgery, the patient should fill this out on the day that they sign the consent for participation (whether it is at the preoperative visit or in the preoperative suite on the day of surgery). The Narcotic Diary will be given to patient with the instructions to fill out after surgery and to document all narcotic pills used including provided and any additional.
- Randomization
 - Arm 1: 64 patients; Arm 2: 64 patients

Visit 3

- Postoperative Day 1
 - Obtain Likert-pain scale score between 18-24 hours post-surgery

Visit 4

- Postoperative Visit (14 days +/- 3 days)
 - Narcotic Diary collected
 - Second Brief Pain Inventory Questionnaire given to patient to complete

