3 OBJECTIVES AND ENDPOINTS

OBJECTIVES	ENDPOINTS	JUSTIFICATION FOR ENDPOINTS
Primary Difference in Likert-pain scale score difference between pre-incision versus post-incision subcutaneous infiltration with 4-5mL 0.25% Bupivacaine at 18-24 hours postoperatively	Likert-pain scale score difference between pre-incision and post-incision subcutaneous infiltration at 18-24 hours postoperatively.	To determine if timing of local anesthetic affects postoperative pain scores.
Secondary To compare total narcotic usage over two weeks	Total number of narcotic tablets used in the first two weeks postoperatively between pre-incision and post-incision subcutaneous infiltration with 4-5mL 0.25% Bupivacaine	To decrease postoperative narcotic usage
Secondary Compare brief pain inventory questionnaire survey score	To compare score levels of the brief pain inventory questionnaire at POD14 between the two study groups	To decrease pain score for patient post surgery

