 - Postoperative pain medication will be ordered for each patient as per standard enhanced recovery protocol
 - On Postoperative Day 1, the patient will be asked her pain scale on the Likert-pain scale. The Likert-pain scale is a 0-10 discrete integer scale. The investigators will check for patient's pain medication use before questionnaire administration. If a patient has received postoperative pain medication, the questionnaire will be administered at least 1.5 hours after the patient has received the pain medication.
 - Discharge medications will be ordered for each patient as per standard enhanced recovery protocol
 - The Brief Pain Inventory Questionnaire will be given to the patient at the 2 -week postoperative visit to be filled out and collected at the postoperative visit.
 - The Narcotic diary (in which the patient writes down how many narcotic tablets they have used per day since the surgery (provided and additional included) will be collected at the postoperative visit.

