9. STATISTICAL CONSIDERATIONS

9.1 STATISTICAL HYPOTHESES

- Primary Efficacy Endpoint(s):
 - Assessment of infiltration at pre-incision (pre) and infiltration at post-incision (post) associated pain score using a Likert-pain scale. The Likert-like pain scale is a validated, subjective measure for acute and chronic pain. The primary endpoint of pain score measurement will take place on postoperative day 1 (18-24 hr post-surgery, postoperative day 1). Scores are recorded by choosing an integer only number on a 0-10 scale that represents between “no pain” and “worst pain”.
- Secondary Efficacy Endpoint(s):
 - The need for additional narcotic usage over 2 weeks between the 2 arms
 - Compare questionnaires between the initial brief pain inventory questionnaire (pre-surgery) and postoperative brief pain inventory questionnaire

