9.4.2 ANALYSIS OF THE PRIMARY EFFICACY ENDPOINT(S)

Analysis of the primary outcome: For the primary outcome, which we assume will be normally distributed, the two independent sample t test comparing two independent groups will be used to compare the pain scores from study arms at POD1. In the event that normal assumption does not hold, a suitable data transformation (e.g., arcsine square-root, logit) will be applied.

A 95%, two-tailed confidence interval for the difference of mean pain scores between the two arms will be constructed. If both upper and lower confidence intervals lay within the ± 1 -unit margin, we will conclude that the pain scores associated with the two routes of wound infiltration are equivalent. Otherwise, we cannot conclude that the effects between the two modes of wound infiltration on postoperative pain are equivalent.

As per ICH E-9 guidelines, a supporting analysis will be conducted whereby analysis of covariance (ANCOVA) will be used to compare the two groups, adjusting for nuisance covariates.

All continuous secondary outcomes will be analyzed using two sample t-test or Mann-Whitney test depending on whether normal assumption holds or not. ANCOVA will be used adjusting for baseline values and other associated covariates and will be considered as supportive analysis.

All categorical secondary outcomes will be analyzed using chi-square test for proportions or Fisher's exact test, as appropriate.

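### The synopsis and Section 3 define the narcotic secondary endpoint as total tablets over two weeks, but 9.1 and 9.4.3 put a yes/no request for more pills in its place, and nothing reconciles the two

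*Combined protocol and SAP*

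**What the plan says.** The documents describe the narcotic outcome in two ways.

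- **An amount.** The synopsis gives the secondary objective as "Total narcotic use over two weeks between patients who received pre-incisional versus post-incisional local anesthetic", and its endpoint row repeats that quantity. The endpoint column of the Section 3 table makes it a count: "Total number of narcotic tablets used in the first two weeks postoperatively". Data collection fits this. The schema (1.2) instructs each woman to "document all narcotic pills used including provided and any additional", and Section 4.1 describes a diary in which "the patient writes down how many narcotic tablets they have used per day since the surgery".
- **A yes/no event.** Section 9.1, under the secondary efficacy endpoints, lists "The need for additional narcotic usage over 2 weeks between the 2 arms" and no tablet total. Section 9.4.3 then states that "The need for additional narcotic usage is a binary-coded variable". The event is a request for narcotics beyond the 12 pills given at discharge, and the arms are compared on the percentage making one, by chi-square or Fisher's exact test. The same section gives this variable formal standing: "The needs for extra amount of pain reliever is an indicator of pain level and a secondary aim of the current study".

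One general sentence, in 9.4.2 and again in 9.4.5, covers outcomes not treated individually: "All continuous secondary outcomes will be analyzed using two sample t-test or Mann-Whitney test depending on whether normal assumption holds or not". It names no narcotic variable.

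**The concern.** The section written to specify the secondary analyses sets out a different variable from the one that the synopsis and Section 3 call the endpoint. The variable that the diary was designed to capture is not named anywhere in Section 9. The variable that is analysed in detail has no stated source record: the diary holds pills used, whereas 9.4.3 counts requests.

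If this stays, either result could be presented after unblinding as the narcotic finding, each with support in the protocol. The two can point in different directions, and nothing in the plan says which one counts.

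**Working it through.** **Step 1. The plan's only computed figure.** Section 9.2 gives a difference of 1 point, SD 2, two-sided alpha 0.05 and power 0.80. By the normal approximation, n per arm = 2 x (1.960 + 0.842)^2 x 2^2 / 1^2 = 62.8, rounded up to 63. The t-test calculation gives 63.77, rounded up to 64, with power 0.801. The stated 64 per arm reproduces. It rests on POD1 pain alone, so the choice of narcotic variable does not touch it.

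**Step 2. The sections side by side.**

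| Section | Narcotic variable | Type |
|---|---|---|
| 1.1 Synopsis | total use over two weeks | amount |
| 3 Endpoint table | number of tablets, first two weeks | count |
| 1.2 and 4.1, diary | pills used per day, supplied and additional | count |
| 9.1 | need for additional narcotics | not typed |
| 9.4.3 | request beyond the 12 discharge pills | yes/no |
| 9.4.2 and 9.4.5, general rule | none named | continuous |

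No section says that the two variables are separate endpoints, ranks them, or lets one replace the other.

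**Step 3. Are they interchangeable?** No. Totals of 0 and 12 tablets both map to *no* if the woman does not ask for more. In the other direction, a woman may ask for more and not take them. This needs no distributional assumption.

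**Step 4. How often could the two disagree?** The documents give no tablet distribution, request rate or expected effect, so everything here is assumed. Set-up: 64 per arm, two-sided 0.05, 10,000 simulated trials per setting, and a total above 12 tablets as a rough proxy for a request. The tests are Mann-Whitney on tablets, and uncorrected chi-square (Fisher if any expected count is below 5) on the yes/no variable.

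| Assumed setting (k = negative-binomial shape) | Mann-Whitney power | Yes/no power | Different verdicts |
|---|---|---|---|
| Means 8 vs 5, k = 1.5 | 74.3% | 59.8% | 29.5% |
| Means 8 vs 5, k = 1 | 55.9% | 48.6% | 29.8% |
| Means 6 vs 3.5, k = 1 | 65.7% | 49.1% | 36.8% |
| 35% non-users, users 10 vs 6.5, k = 2 | 23.7% | 45.5% | 32.0% |
| 40% non-users, users 10 vs 6, k = 2 | 25.8% | 55.4% | 38.2% |
| 50% non-users, users 12 vs 7, k = 2 | 16.8% | 50.9% | 38.3% |
| Heavy users 25% vs 8% (mean 18, others 4), k = 2 | 25.3% | 37.4% | 28.9% |

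Repeat runs with fewer trials put the last column at 28-39%. All seven settings assume a sizeable true difference. In four settings with none (negative binomial with mean 8 or mean 5, k = 1.5; 40% non-users; a heavy-user mixture), the verdicts differ in only about 7-9% of trials.

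**Step 5. Which test and estimate go together?** In the three non-user settings the true mean differences are 0.65 x 3.5 = 2.28, 0.60 x 4 = 2.40 and 0.50 x 5 = 2.50 tablets. Yet the Hodges-Lehmann shift is exactly 0 in 62%, 75% and 96% of trials, so it can be a poor estimate here. Reporting Mann-Whitney beside a bootstrap confidence interval for the mean difference, with equal standing, gives conflicting verdicts in 13-37% of trials across the seven settings. One of them has to govern.

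**Step 6. The diary window.** The last visit is at 14 +/- 3 days, so it falls on days 11 to 17. Late visits can add up to 17 - 14 = 3 days beyond two weeks. Visits on days 11, 12 and 13 leave 3/14 = 21.4%, 2/14 = 14.3% and 1/14 = 7.1% of the days uncollected, even if the hand-in day is counted as complete. A diary handed in on day 11 is certain to be complete only through day 10.

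**The case against.** The best defence is that the plan is less bare than it looks. The synopsis and Section 3 do label total tablets as the endpoint. The general rule in 9.4.2 and 9.4.5 gives any continuous secondary outcome a t-test or Mann-Whitney, with ANCOVA in support. The yes/no request could be read as an additional outcome. For its source, the diary separates supplied from additional pills, Section 6.4 describes a daily log of tablets, and the Schedule of Activities has a medication review at the last visit.

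Much of this stands. A reader might infer that nothing in the documents identifies the narcotic endpoint, or that tablet counts have no analysis at all. Neither inference is supported: two sections give the label, and the general rule supplies a test.

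The defence does not remove the conflict. A general test does not say which variable is the endpoint. Section 9.1 lists the need for additional narcotics among the secondary efficacy endpoints and leaves tablets out, so the request is not presented as an extra. The diary, the log and the medication review might each show additional use, but use is not a request, and none of them is assigned as the source.

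**Conclusion.** The conflict is real and rests on the text alone. The stated endpoint is total tablets over two weeks. The only narcotic analysis set out in Section 9 is a yes/no request that does not measure it, and no section reconciles or ranks the two. It should be corrected before unblinding, but it concerns a secondary endpoint only.

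Three stronger readings are tempting and do not hold.

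- A reader might infer that the yes/no variable costs power. The documents give no tablet data, and in the simulations the order reverses with the assumed distribution: tablets do better under plain negative-binomial counts, the yes/no variable does better with many non-users or a heavy-user subgroup.
- A reader might take 28-39% as the general rate of conflicting verdicts. That range assumes a sizeable true difference. With none it is about 7-9%, and Sections 2.1 and 9.2 report that clinicians see no obvious difference in pain between the two timings. Both ranges also rest on more than 12 tablets standing in for a request.
- A reader might infer that the trial's main conclusion or size is in doubt. The primary endpoint and the 64 per arm are unaffected.

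**What to change.** In 9.1 and 9.4.3:

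1. Name total diary tablets over the first two weeks as the narcotic secondary endpoint, to match the synopsis and Section 3.
2. Give it one governing analysis whose test and estimate agree. For example, use the difference in mean tablets with its 95% bootstrap confidence interval, judged by whether the interval excludes 0, with Mann-Whitney as supportive.
3. Keep the yes/no request as an outcome labelled supportive, and state which record supplies it.
4. Count tablets only through POD14. As an optional sensitivity analysis for visits on days 11 to 13, compare totals through POD10, the last day certain to be complete for every woman seen within the window.

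The cost is wording in two subsections and, if wanted, one extra analysis of diary data already planned. The tablet endpoint needs no new visits, contacts, data items or patients. The request outcome needs only its source named.

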6.3 MEASURES TO MINIMIZE BIAS: RANDOMIZATION AND BLINDING

- Patient-blinded study
- Multi-site study
- The surgeon at the time of intervention will not be blinded as to which arm the patient belongs
- Randomization will be performed using 1:1 randomization, permuted blocks

Randomization will be accomplished using the Biostatistics Randomization Management System according to hospital site.

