6.5 CONCOMITANT THERAPY

Patients who participate in the study will receive the following standardized pain regimen:

- General anesthesia will be given as per standard protocol
- Preoperative pain medication will be ordered for each patient as per standard enhanced recovery protocol.
- Postoperative pain medication will be ordered for each patient as per standard enhanced recovery protocol.
- Discharge medications will be ordered for each patient as per standard enhanced recovery protocol.

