9.4.5 BASELINE DESCRIPTIVE STATISTICS

Demographic and clinical data (including operative time and procedure performed) will be summarized according to treatment arm using means, S.D.s, medians, quartiles, and proportions, as appropriate. As per ICH E-9 guidelines, no inferential comparisons of the two arms will be carried out.

All continuous secondary outcomes will be analyzed using two sample t-test or Mann-Whitney test depending on whether normal assumption holds or not. ANCOVA will be used adjusting for baseline values and other associated covariates and will be considered as supportive analysis.

All categorical secondary outcomes will be analyzed using chi-square test for proportions or Fisher's exact test, as appropriate.

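### Randomization runs by hospital site, but the yes/no narcotic-request endpoint is tested without site: valid, mildly conservative, and cheap to improve

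*Combined protocol and SAP*

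**What the plan says.** - **Randomization (6.3).** "Randomization will be performed using 1:1 randomization, permuted blocks", and "Randomization will be accomplished using the Biostatistics Randomization Management System according to hospital site". The synopsis (1.1) names eight hospitals in one health system.
- **Endpoint (9.1, 9.4.3).** The endpoint is listed as "The need for additional narcotic usage over 2 weeks between the 2 arms". Section 9.4.3 codes it yes or no. The percentages requesting more medication are to be "compared in a 2 by 2 contingency table format using chi-square test" or Fisher's exact test.
- **Other secondary analyses (9.4.2, 9.4.5).** Continuous outcomes get a supportive model: "ANCOVA will be used adjusting for baseline values and other associated covariates". Binary outcomes get no counterpart: "All categorical secondary outcomes will be analyzed using chi-square test for proportions" or Fisher's exact test.
- **Discharge medication (9.4.3, 6.5).** "All patients will be discharged with 12 standard narcotic pills", and "Discharge medications will be ordered for each patient as per standard enhanced recovery protocol".
- **Elsewhere.** Sections 9.4.7 and 9.4.9 plan no subgroup or exploratory analyses, so site does not enter there either.

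**The concern.** Balancing the arms within each hospital means that differences between hospitals largely cancel from the comparison of arms. A pooled 2 by 2 test ignores this. Its standard error uses the overall request rate, which includes the spread between hospitals. When hospitals differ, that standard error is too large for the design, the test rejects less than 5% of the time under no effect, and some power is lost.

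Bias and false positives are not at stake; the cost is precision on one secondary endpoint. The supportive ANCOVA does not recover it. Its covariates are not listed, so site could be among them, but it is planned only for continuous outcomes.

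**Working it through.** **The plan's own figure.** The only sample size is for postoperative day 1 pain (9.2): difference 1, SD 2, two-sided alpha 0.05, power 0.8. The normal approximation, 2 × (1.96 + 0.842)² × 2² / 1² = 62.8, rounds up to 63 per arm. The t-test version gives 63.77, so 64 per arm, with power 0.801. The stated 64 per arm (128 in total) is reproduced. The plan gives no request rate or power for the narcotic endpoint, so there is no figure of its own to reproduce there.

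**Inputs.** From the documents: 128 patients, eight sites, 1:1 permuted blocks, two-sided 5%. Assumed: request rates, odds ratios, spread between sites, patients per site, and block size where it matters (4).

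**Formulas.**
- Pooled test: z = (p1 − p0) / √[p̄(1 − p̄)(1/n1 + 1/n0)].
- Mantel-Haenszel, with x1s requests among n1s patients in one arm of site s, n0s patients in the other arm, and ts requests among Ts patients at the site: z = Σ(x1s − ts·n1s/Ts) / √Σ[ts(Ts − ts)·n1s·n0s / (Ts²(Ts − 1))].
- True size of the pooled test under blocking within equal-sized sites: f = mean[ps(1 − ps)] / [p̄(1 − p̄)], and size = 2[1 − Φ(1.96/√f)].

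**Step 1: fixed site rates, 16 patients per site.** For rates evenly spaced from 10 to 30%, p̄ = 0.20 and the variance between sites is 0.0043. Then f = (0.16 − 0.0043)/0.16 = 0.973 and the size is 4.7%. Other patterns, with simulation (100,000 runs for size, 40,000 for power at odds ratio 3):

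| Site rates | f | Size by formula | Chi-square, simulated | Fisher, simulated | Mantel-Haenszel, simulated | Power, chi-square v Mantel-Haenszel |
|---|---|---|---|---|---|---|
| all 20% | 1.000 | 5.0% | 4.8% | 3.0% | 4.9% | 80.9 v 80.5% |
| 10–30% | 0.973 | 4.7% | 4.6% | 2.7% | 5.0% | 78.1 v 78.8% |
| 5–45% | 0.909 | 4.0% | 4.1% | 2.4% | 4.9% | 75.6 v 78.4% |
| half 5%, half 50% | 0.746 | 2.3% | 2.5% | 1.3% | 5.0% | 52.4 v 67.2% |

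The last row is a stress case. Fisher's shortfall is partly its own discreteness.

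**Step 2: random site effects, 16 patients per site.** Site effects are normal on the logit scale, the odds ratio is constant, and there are 100,000 replicates. The ranges in the first column show roughly one SD either side of the centre. Entries are chi-square v Mantel-Haenszel, in %.

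| Control rate, logit SD | Type I error | Power |
|---|---|---|
| 20%, SD 0 | 4.8 v 4.9 | OR 3: 80.9 v 80.6 |
| 20%, SD 0.5 (12–28%) | 4.4 v 4.9 | OR 1.5: 14.7 v 15.6; OR 2: 37.2 v 38.4; OR 3: 77.1 v 77.9 |
| 20%, SD 1.0 (7–34%) | 3.6 v 4.9 | OR 2: 29.4 v 34.1; OR 3: 67.1 v 71.8 |
| 40%, SD 0.5 (28–52%) | 4.6 v 5.0 | OR 2: 44.3 v 47.4; OR 2.6: 71.4 v 74.1 |
| 40%, SD 1.0 (18–62%) | 3.3 v 4.8 | OR 2.6: 61.0 v 67.9 |
| 10%, SD 0.5 (6–14%) | 4.9 v 5.0 | OR 3: 58.2 v 59.7 |
| 10%, SD 1.0 (3–17%) | 4.2 v 5.0 | OR 3: 49.3 v 54.0 |

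Over control rates of 5 to 40% and odds ratios of 1.5 to 3, the Mantel-Haenszel gain is -1.0 to +0.6 points at SD 0 and +0.2 to +3.1 at SD 0.5. At SD 1.0 it is +4.7 to +6.9 for rates of 20 to 40% with odds ratio 2 to 3, and +1.0 to +4.7 for rates of 5 to 10%. Mantel-Haenszel type I error stays at 4.7 to 5.1%.

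**Step 3: precision with no true effect.** The ratio of the crude to the Mantel-Haenszel standard error of the risk difference (percentage points) is:
- 20% rate: 6.97/6.85 = 1.02 at SD 0.5, and 6.91/6.49 = 1.06 at SD 1.0.
- 40% rate: 8.56/8.35 = 1.03 at SD 0.5, and 8.50/7.81 = 1.09 at SD 1.0.

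The mean arm difference is within 0.1 points of zero in every case, so there is no bias.

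**Step 4: uneven recruitment.** Sites of 40, 28, 20, 14, 10, 8, 5 and 3, blocks of 4, sites under 8 pooled, rates 10, 20 and 40%. Mantel-Haenszel type I error is 4.8 to 5.1%. The gain is -0.7 to +0.8 points (SD 0), +0.2 to +2.4 (SD 0.5) and +1.0 to +6.1 (SD 1.0).

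**Step 5: if randomization is not stratified by site.** With the same uneven sizes, chi-square type I error is 4.8 to 5.3%, Mantel-Haenszel 4.7 to 5.1%, and the power change is -2.6 to +4.3 points.

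**The case against.** The strongest reply is that this is a preference and not an error. The planned test is valid, errs on the safe side, and serves an endpoint for which the plan makes no power claim.

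- **Likely size.** One health system, a shared recovery protocol and the same 12 pills for everyone point to similar request rates. That stands, and it is why the realistic gain is small.
- **Reading of 6.3.** The section never uses the word stratified, and 4.1 describes the scheme without mentioning site. That stands as a condition: step 5 shows that the conservatism disappears if site was not a stratification factor. Permuted blocks run by site are still most naturally read as stratification.
- **Endpoint definition.** The synopsis and section 3 define the narcotic outcome as total use over two weeks. That version would be continuous and could reach the supportive ANCOVA. This also stands: the point concerns only the yes/no version in 9.1 and 9.4.3.
- **Fisher's exact test.** The plan allows it, and at a 5% rate 64 per arm gives 64 × 0.05 = 3.2 expected requests per arm, where Fisher would conventionally apply. But Fisher is more conservative still, and Mantel-Haenszel holds 4.7 to 5.1% even at that rate.
- **Pooling cutoff.** The threshold of 8 patients is a convention. Type I error holds under it in the uneven layout tried.

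None of this supplies an analysis of the endpoint that uses the randomization factor.

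**Conclusion.** The point holds and is minor. If 6.3 means stratification by site, the unadjusted test of narcotic requests is unbiased and does not inflate type I error, but it is conservative to the extent that hospitals differ. Moderate differences cost at most about 3 points of power. Large ones cost up to about 7, but nothing in the documents suggests differences of that size. For small effects power is low under either test (20% rate, odds ratio 1.5, SD 0.5: 14.7 v 15.6%), so stratifying does not rescue the endpoint. Request rates, odds ratios, site spread, site sizes and block size are all assumptions. What the documents themselves establish is that no planned analysis of this endpoint uses site.

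**What to change.** In 9.4.3, replace the single-table test with a Mantel-Haenszel test stratified by hospital site, without continuity correction. Report the Mantel-Haenszel common risk difference with a 95% CI. Pool sites with fewer than 8 patients into one stratum, and keep the crude percentage per arm as description. Settle this before outcome data are seen, so that adjustment is not a later choice.

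The cost is one line of text. No new data are needed, because site is known from randomization. The downsides are sparse strata at low-recruiting sites, which the pooling rule handles, and up to about 1 point of power if hospitals do not differ at all (up to 2.6 points in the scenarios where randomization was not stratified by site).
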